6.9.1.6 Safety Parameters

Safety endpoints are:

- AEs
- ADRs
- Hypoglycaemic episodes
- Cardiovascular events
- laboratory measurements
- Vital signs (blood pressure, pulse rate and body temperature)
- 12-lead ECG

All safety summaries will be performed on the Safety Analysis Set. No formal statistical test would be performed to determine statistical significance between treatment groups.

6.9.2 Subgroup Analyses

Change in HbA1c from baseline to Week 24 will be analysed for the subgroup of baseline characteristics.

6.9.3 Interim Analyses

No interim analysis is planned.

6.9.4 Determination of Sample Size

[REDACTED]

[REDACTED]

[REDACTED]

7. Study Report and Publication Policy

Any formal presentation or publication of data from this trial will be considered by the appropriate sponsor personnel. For multi-centre studies it is mandatory that the first publication is based on data from all centres, analysed as stipulated in the protocol. Investigators agree not to present data gathered from one centre or a small group of centres before the full publication. In any case, the Sponsor will review any publications/communications/abstracts for accuracy (thus avoiding potential discrepancies with submissions to health authorities), verify that proprietary, confidential information is not being inadvertently divulged, and provide any relevant supplementary information.

8 References

[1] EMA 2012

Guideline on clinical investigation of medicinal products in the treatment or prevention of diabetes mellitus 14 May 2012 CPMP/EWP/1080/00 Rev. 1 Committee for Medicinal Products for Human Use (CHMP)

[2] ADA 2014

Diagnosis and Classification of Diabetes Mellitus. Diabetes Mellitus, Volume 36, Supplement 1, January 2014, S81-90

1 LIST OF ABBREVIATIONS AND DEFINITIONS OF TERMS

Table 1: Abbreviations and Definitions of Terms

ADR(s)	Adverse Drug Reaction(s)
AE(s)	Adverse Event(s)
ANCOVA	Analysis of Covariance
ATC	Anatomical Therapeutic Chemical
BDRM	Blinded Data Review Meeting
BMI	Body Mass Index
CFDA	China Food and Drug Administration
CI	Confidence Interval
CIP	Clinical Investigational Plan
CRF	Case Report Form
DPP-4	Dipeptidyl Peptidase-4
EAC	Event Adjudication Committee
ECG	Electrocardiogram
eCRF	Electronic Case Report Form
FAS	Full Analysis Set
FDA	Food and Drug Administration
FPG	Fasting Plasma Glucose
FV	Follow-up Visit
GGT	Gamma-Glutamyl Transferase
GIP	Glucose-dependent Insulinotropic Peptide
GLP-1	Glucagon Like Peptide-1
HbA1c	Glycosylated Fraction of Haemoglobin
HDL-C	High Density Lipoprotein Cholesterol
HR	Heart Rate
hr(s)	hour(s)
HOMA- β	Homeostatic Model Assessment-Beta
HOMA-IR	Homeostatic Model Assessment-Insulin Resistance
IB	Investigator's Brochure
IRB	Institutional Review Board
IWRS	Interactive Web Response System
Kg	Kilograms
LDH	Lactate Dehydrogenase
LDL-C	Low Density Lipoprotein Cholesterol
LOCF	Last Observation Carried Forward
LS-Mean	Least Square Mean
m	Metre
Max	Maximum
MedDRA	Medical Dictionary for Regulatory Activities

Mg	Milligram
Min	Minimum
MMRM	Mixed Model Repeated Measure
QTc	Q-T interval corrected for heart rate
N	Number of subjects
OR	Odds Ratio
RV	Randomization Visit
PPS	Per-Protocol Set
PT	Preferred Term
PV	Placebo Run-In Visit
SAE	Serious Adverse Event
SAP	Statistical Analysis Plan
SAS®	Statistical Analysis Software
SD	Standard Deviation
SE	Standard Error
SOC	System Organ Class
SV	Screening Visit
TEAE	Treatment Emergent Adverse Event
WHO	World Health Organization

2 INTRODUCTION

This Statistical Analyses Plan (SAP) describes the planned analyses to evaluate the efficacy and safety of MP-513 compared with placebo in Chinese subjects with type 2 diabetes mellitus inadequately controlled with metformin monotherapy accompanying diet and exercise.

The general information about the study is detailed in the MP-513-C03 protocol.

3 STUDY OBJECTIVES

[figure not shown]
The objective of this study is to evaluate the efficacy and safety of MP-513 compared with placebo in Chinese subjects with type 2 diabetes mellitus inadequately controlled with metformin monotherapy accompanying diet and exercise.

4 STUDY DESIGN

4.1 General Design

This is a multi-centre, randomized, double-blind, placebo-controlled, parallel-group study in subjects with type 2 diabetes mellitus.

The study flowchart is presented below:

4.2 Discussion of Study Design

The main characteristics of this study are:

- **Placebo run-in period:** The intention of the placebo run-in period is to exclude subjects who have poor treatment compliance, to enable a comparison of the effects of different treatments without the influence of placebo effect and to have a relatively stable HbA1c value at baseline.
- **Duration of double-blind treatment period:** HbA1c stabilizes over 24-week period. The double-blind treatment period is planned for 24 weeks to evaluate a stable HbA1c change from baseline compared with placebo and to investigate the safety/tolerability of MP-513 after treatment for this duration.
- **Dosage:** The dose of 20 mg orally administered once daily before breakfast is the established dose for this medication.
- **Metformin Combination:** The metformin is considered the most prescribed oral diabetes drug that does not cause hypoglycaemia or weight gain. Considering MP-513 could serve as a new add on treatment which is considered to be safe and can also be expected to increase efficacy of antidiabetic treatment, i.e. this combination has a clearly positive risk-benefit ratio. Also, the subjects will be protected against their diabetes with a well-established standard regimen during the trial.
- **Safety Follow-up:** The two week safety follow-up period is sufficient to confirm the subjects' safety after the completion/discontinuation of the treatment.

4.3 Method of Assignment of Subjects to Treatment Groups

Treatment assignment will be managed through static blocked randomization and an Interactive Web Response System (IWRS) will be used.

After the Placebo run-in period, the eligible subjects will be randomized to one of the following treatment groups in a 1:1 allocation ratio:

- **Test Product:** One 20 mg tablet of MP-513, once daily before breakfast starting from the randomization visit (Day 1).
- **Placebo:** One placebo tablet, once daily before breakfast starting from the randomization visit (Day 1).

Randomization will be performed according to computer generated randomization scheme where a treatment group designation has been assigned to each subjects' randomization kit number. The treatment designation will remain blinded until the database is closed. An independent unblinded team within [REDACTED] will hold the randomization codes throughout the study, until authorization is provided by a Mitsubishi Tanabe Pharma Corporation representative to release the randomization schedule.

4.4 Blinding

Study treatments will be packaged for double-blind administration. The placebo is identical to the corresponding active treatments.

During single-blind run-in period, the subjects will not know that they are receiving placebo during the single-blind run-in period.

During the double-blind treatment period the subject, the investigator, the laboratory personnel, and the sponsor other than a designated person would not know the treatment arm to which a subject is assigned.

Unblinding of treatment for a subject may be performed in case investigator considers it necessary for the safety of the subject. The reason for breaking the blind along with date and time must be clearly documented in the source documentation and Case Report Form (CRF), and the subject will be discontinued from the study. The sponsor must be notified immediately upon all unblinding situations.

4.5 Determination of Sample Size

The sample size was estimated based on the primary efficacy variable for assessing treatment difference in mean change in HbA1c from baseline at Week 24 between MP-513 and placebo. The data used for samples size calculation was based on the studies of MP-513 in Japan and other Dipeptidyl Peptidase-4 (DPP-4) inhibitors in China. For a two sided t-test of difference with 0.05 significance level and 90% power of test, 86 subjects per treatment group is required to detect a treatment difference of 0.5% in mean change in HbA1c from baseline at Week 24 with a common standard deviation of 1.0%.

Considering the drop-out rate of 30% and China Food and Drug Administration (CFDA) (on drug registration Code 28) requirement of at least 100 pairs of subjects to be enrolled in a phase 3 study, a total of 240 subjects (120 subjects per treatment group) are required to be randomized in this study.

5 CHANGES IN THE CONDUCT OF THE STUDY OR PLANNED ANALYSES

5.1 Changes in the Conduct of the Study

This SAP is prepared based on the study protocol version 2.0 dated 29 April, 2016. A typographical error has been observed in the protocol version 2.0, the window of Follow-up Visit (FV) was wrongly mentioned as Week 26 + 7 days which is corrected as Week 26 + 14 days. A note to file has been issued on 01July, 2016 to incorporate this modification.

There are no other planned changes either in the conduct of the study or planned analysis at the time of preparing this SAP.

6 BASELINE, EFFICACY AND SAFETY EVALUATIONS

6.1 Schedule of Evaluations

The assessments to be conducted at each scheduled visit are displayed in the below table.

Table 2 Schedule of Visits

Period	Scr. Period	Placebo Run-in Period	Double-Blind Treatment Period						Follow-up Period	
Visit	SV	PV	RV	V1	V2	V3	V4	V5	V6	FV
Visiting Windows	Day -28 +/- 3 days	Day -14 +/- 3 days	Day 1	Week 4 +/- 7 days	Week 8 +/- 7 days	Week 12 +/- 7 days	Week 16 +/- 7 days	Week 20 +/- 7 days	Week 24 ⁽⁵⁾ +/- 7 days	Week 26 ⁽⁶⁾ + 14 days
Items										
Obtain written informed consent	X									
Screening/Inclusion/Exclusion criteria evaluation	X	X	X							
Demographics and complete medical history	X ⁽⁷⁾									
Height	X									
Body Weight	X		X	X	X	X	X	X	X	
Vital signs ⁽¹⁾	X	X	X	X	X	X	X	X	X	
12-lead ECG	X		X			X				X
Routine laboratory evaluations: hematology, chemistry, urinalysis	X		X	X	X	X	X	X	X	
Serum pregnancy test ⁽²⁾	X									X
HbA1c	X	X	X	X	X	X	X	X	X	
Fasting plasma glucose	X	X	X	X	X	X	X	X	X	
Fasting insulin, C-peptide and glucagon			X	X	X	X	X	X	X	
Dispense medication			X	X	X	X	X	X	X	
Return of unused medication				X	X	X	X	X	X	X
Assessment of adverse events ⁽³⁾ and concomitant medication	X	X	X	X	X	X	X	X	X	X
Hypoglycaemic episodes ⁽⁴⁾	X	X	X	X	X	X	X	X	X	X
Dispense subjects diary and glucometer	X									
Subject diary review		X	X	X	X	X	X	X	X	

Scr period: Screening period, SV: Screening visit, PV: Placebo run-in visit, RV: Randomization visit, FV: follow-up visit

(1) Vital signs (sitting blood pressure, pulse rate and body temperature)

(2) The serum pregnancy test will be performed only for female subjects of childbearing potential.

(3) AEs will be collected and reported on the eCRF from the date of informed consent to 14 days after the final dose of the study drug considering the half-life (T1/2) of MP-513.

(4) The occurrence of hypoglycaemic episodes will be recorded continuously throughout the study by a subject diary

(5) These assessments will also be performed at early termination.

(6) Telephone visit

(7) Including physical examination

6.2 Time Point Algorithms

6.2.1 Study Day

The date of first dose of study drug administration during the double blind phase will be considered study day 1, and the day before the first dose of study drug of double blind phase will be study day -1. Study days will be calculated only when the full assessment date is known (i.e., partial dates will have missing study days).

$$\text{Study Day} = \begin{cases} \text{Date of Assessment} - \text{Date of Randomization Visit} + 1 \\ \quad \text{For assessment on or after the day of randomization} \\ \text{Date of Assessment} - \text{Date of Randomization Visit} \\ \quad \text{For assessment before the day of randomization} \end{cases}$$

6.2.2 Windows

For the purpose of effectiveness and safety analysis, all scheduled and unscheduled clinic visits will be windowed as presented in the below table. The planned protocol visit window will be used for analysis.

Table 3 Schedule of Visits

Visit	Week	Scheduled Study Day	Visit Window in Protocol (Days)
Randomization Visit (RV)	Randomization Visit (RV)	1	1
Visit 1	Week 4	28	21 – 35
Visit 2	Week 8	56	49 – 63
Visit 3	Week 12	84	77 – 91
Visit 4	Week 16	112	105 – 119
Visit 5	Week 20	140	133 – 147
Visit 6	Week 24	168	161 – 175
Follow-up Visit	Week 26	182	182 – 196

If a visit day is outside of these windows, then it is considered as non-windowed, otherwise it is windowed. If a subject has more than one assessment occurring in the same visit window, the data from the visit closest to the scheduled study day will be used. If two visits have the same distance from the scheduled study day, the data of the visit after the scheduled study day will be used.

The unscheduled visits will be chronologically arranged between two scheduled visits. The unscheduled visits will be numbered sequentially with an increment of 0.1 to the visit number corresponding to scheduled visit preceding the unscheduled visit. For example, if two unscheduled visits occur between visit 1 (visit number is 10) and visit 2 (visit number is 20), then these unscheduled visits will be numbered 10.1, 10.2 in the order they occurred.

The assessments made in unscheduled visits will be considered in imputation of missing assessment using Last Observation Carry Forward (LOCF) method for Week 12 or Week 24.

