7.3 Handling of Dropouts or Missing Data

Subjects who discontinue the study prior to or after the initiation of the study drug will not be replaced and available data of these subjects until the point of discontinuation will be summarized. The missing baseline assessment will not be imputed.

For categorical variables with missing values, a category documenting the frequency of missing values will be displayed in the summary tables.

The missing HbA1c and FPG value at week 12 or week 24 will be imputed using last observation carried forward (LOCF) approach. Baseline value will not be used to impute missing data. The missing data of Fasting insulin, C-peptide, Glucagon, HOMA-IR, HOMA- β and Body weight at week 24 will also be imputed using LOCF approach.

The supportive analysis for primary efficacy will be done using observed values.

There will be no imputation of missing values in database of safety data, however missing relationship between AE and study medication will be considered as related to treatment following worst case principle. Missing severity of an AE will be summarized as severe AE.

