8.8.2 Clinical Laboratory Evaluations

Laboratory results (hematology and blood chemistry) will be summarized by treatment groups using descriptive statistics for observed and change from baseline values for all the post baseline assessments visits. The categorical parameters from urinalysis will be summarized by frequency counts and percentages.

Additionally, shift tables will be produced. The shift tables will be based on the classification of laboratory results i.e. Low/Normal/High of post baseline visits compared to the grading of baseline results.

A full subject listing will be presented for laboratory results.

Serum pregnancy test results for female subjects will be listed.

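### Laboratory tables keep one value per visit window and plan no worst post-baseline shift, so some abnormal results can be missing from every laboratory summary

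*SAP*

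**What the plan says.** SAP 6.2.2 sets one windowing rule for the whole analysis: "For the purpose of effectiveness and safety analysis, all scheduled and unscheduled clinic visits will be windowed". Each of Visits 1 to 6 has a window of 7 days either side of its scheduled study day. Where several assessments share a window, "the data from the visit closest to the scheduled study day will be used". Where two are equally distant, "the data of the visit after the scheduled study day will be used".

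A visit on any other day is only given a label: "If a visit day is outside of these windows, then it is considered as non-windowed, otherwise it is windowed". The section gives unscheduled results one further use: "The assessments made in unscheduled visits will be considered in imputation of missing assessment using Last Observation Carry Forward (LOCF) method", at Week 12 or Week 24. SAP 7.3 closes that route for laboratory safety data: "There will be no imputation of missing values in database of safety data".

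SAP 8.8.2 plans by-visit descriptive statistics for haematology and chemistry, plus shift tables: "The shift tables will be based on the classification of laboratory results i.e. Low/Normal/High of post baseline visits", set against the baseline grade. It also plans a full laboratory listing. It names no worst post-baseline value and no count of subjects abnormal at any time.

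**The concern.** Taking the value nearest the target day makes sense for an efficacy endpoint tied to a fixed time. A safety shift table is usually read for a different purpose: how many subjects in each arm became abnormal at some point on treatment. Under SAP 6.2.2, calendar distance decides which laboratory value represents a visit, and the abnormality of the value plays no part.

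This works against abnormal results in three ways:

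- An abnormal check can lose to a normal value nearer the target day.
- An abnormal scheduled value can be replaced by a normal recheck. Rechecks are foreseen, because Protocol 6.6.2.4 requires clinically significant laboratory abnormalities to be followed until they resolve, stabilise or cease to matter.
- A result between windows belongs to no visit, so a by-visit table has no stated row for it.

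At stake is the laboratory safety comparison between arms (for example ALT, creatinine or creatine kinase). The primary efficacy conclusion is not affected.

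**Working it through.** **Inputs.** Scheduled days 28, 56, 84, 112, 140 and 168 with their windows (SAP 6.2.2, Table 3); the closest-day and tie rules (SAP 6.2.2); 240 subjects and a 30% drop-out allowance (SAP 4.5).

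**1. The plan's windows.** Scheduled day ± 7 gives 21–35, 49–63, 77–91, 105–119, 133–147 and 161–175. All six agree with Table 3.

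**2. Selection inside the Week 8 window (target Day 56).** Distance = |study day − 56|.

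| Results in window | Distances | Value used | Effect |
|---|---|---|---|
| Day 56 normal, Day 60 high | 0 and 4 | Day 56 | high value not tabulated |
| Day 53 high, Day 59 normal recheck | 3 and 3 (tie) | Day 59 | high value not tabulated |
| Day 50 high, Day 55 normal recheck | 6 and 1 | Day 55 | high value not tabulated |

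**3. How often an unscheduled check is the value used.** This counts the 14 other days of a window on which an unscheduled check would beat the scheduled visit.

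| Scheduled visit relative to target | Unscheduled check wins on |
|---|---|
| on target | 0 of 14 days |
| 3 days early / 3 days late | 6 / 5 of 14 days |
| 7 days early / 7 days late | 14 / 13 of 14 days |

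Assume scheduled visits are spread evenly and the check is equally likely on any other day of the window. The unscheduled check is then the one used in 7% of cases if scheduled visits fall within 1 day of target, 21% within 3 days and 50% within 7 days. A check that is alone in its window is always used.

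**4. Days in no window.** Days 2 to 175 are 174 days. The windows cover 6 × 15 = 90. The remainder is 174 − 90 = 84, and 84/174 = 48%. The gaps are Days 2–20 (19 days) and 36–48, 64–76, 92–104, 120–132 and 148–160 (13 days each): 19 + 5 × 13 = 84.

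**5. Early-termination panels.** The schedule of visits (footnote 5) repeats the Week 24 assessments at early termination, on whatever day the subject stops. Assume that those days are spread evenly over Days 2 to 175:

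- at the planned 30% drop-out, 0.30 × 240 = 72 subjects, and 72 × 84/174 ≈ 35 panels in no window;
- at an assumed 10%, 24 × 84/174 ≈ 12 panels.

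Filing them under Visit 6 would conflict with the day-based windows. The SAP does not say which applies.

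**6. What by-visit shift tables can show.** At most six values per subject and parameter enter. If the six visits show h1 to h6 subjects High in an arm, the number High at any of those visits lies between the largest h and h1 + … + h6. The tables cannot narrow this range, and values dropped in steps 2, 4 and 5 lie outside it altogether.

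**The case against.** A reader might infer that abnormal results from unscheduled checks never enter a summary or shift table. The documents do not support that. SAP 6.2.2 expressly windows unscheduled visits, and step 3 shows that they are used when closest, later in a tie or alone in the window. Nor do the documents say that unscheduled tests usually lie further from the target day than scheduled ones.

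Four further objections carry weight:

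- **Adverse event tables.** Protocol 6.6.2.4 counts a clinically significant laboratory abnormality as an adverse event, and SAP 8.8.1 tabulates treatment-emergent events whatever the visit window. This covers the most serious results. It depends on the investigator's judgement, however, and where a diagnosis explains the result, the diagnosis is recorded in place of the value. It does not replace a Low/Normal/High count.
- **Listing.** A full laboratory listing is planned, and SAP 6.2.2 gives unscheduled visits their own numbers. A listing gives no count by arm, and SAP 7.1 arranges safety listings by planned visit, so the place of unscheduled results in it is unclear.
- **Table shells.** The SAP contents list table shells in Section 12, which is not in the available text. They could already hold a worst-value row.
- **Design choice.** By-visit shifts are internally consistent, safety is descriptive only, and laboratory tests are already scheduled at all six treatment visits. This limits the harm but does not supply the missing count.

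**Conclusion.** The point holds as a gap in safety reporting that is cheap to close. Followed as written, SAP 6.2.2 and 8.8.2 can leave abnormal laboratory results, scheduled or unscheduled, out of the summaries and shift tables. No table described in the available text counts subjects per arm who were ever Low or High.

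The 48% of study days outside any window follows directly from Table 3. That values on those days go untabulated is an inference from the by-visit layout, because the SAP does not say so outright. The 12 to 35 early-termination panels rest on the assumed drop-out rates and an even spread of stopping days. The documents give no expected number of unscheduled checks and no abnormality rates, so the number of subjects misclassified cannot be estimated. It may be small.

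**What to change.** Keep the closest-visit rule of SAP 6.2.2 for efficacy and for by-visit descriptive statistics. In SAP 8.8.2, add to each shift table a row from baseline grade to worst post-baseline grade, once for the lowest and once for the highest value. This row should use all scheduled, unscheduled and early-termination results whatever their window. Add one sentence saying how non-windowed and early-termination values are treated in the by-visit tables. If the table shells already contain a worst-value row, SAP 8.8.2 should say so.

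The cost is one or two extra rows per table, from data already collected. Somewhat more abnormal shifts will be displayed, since the worst of several values is more often abnormal than a single one. That applies to both arms, so the row should be read as a comparison with placebo.

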6.5.3 Treatment with Metformin

Treatment with metformin (≥ 1000 mg/day) will be continued without any changes to the dosage and/or the dose regimen from at least 8 weeks before the screening visit to the final dose of the study drug. The metformin prescribed in the sites will continue to be prescribed and dispensed during the study.

Subjects may change the dosage and/or the dose regimen after the final dose of the study drug including the early termination if required when judged by the investigator.

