- Subjects are to be instructed that they have to return for the next scheduled visit day.

Treatment Visit 5 (Week 20 plus/minus 7 days of treatment)

The following observations/procedures are to be performed and checked:

- Vital signs, body weight
- Review use of concomitant treatments and of the regular metformin therapy
- Blood and urine is to be drawn and sent to the central laboratory according to the local procedure for evaluation of haematology, clinical chemistry, urinalysis, HbA1c, FPG, fasting insulin, C-peptide and glucagon
- Evaluation for any AEs including hypoglycaemic episodes experienced by the subjects since last visit
- Review subject diary
- MP-513 or placebo will be dispensed to the subjects. Unused medication has to be returned to the site
- Subjects are to be instructed that they have to return for the next scheduled visit day.

Treatment Visit 6 (Week 24plus/minus 7 days of treatment /Early termination visit: date of discontinuation* plus 7 days)

*Date of discontinuation is defined as the date of decision of discontinuation for subjects by the investigator.

This visit is the regular **end of treatment visit**. In case of premature termination, the same evaluations have to be performed as **the early termination visit**.

The following observations/procedures are to be performed and checked:

- Vital signs, body weight and ECG
- Review use of concomitant treatments and of the regular metformin therapy
- Blood and urine is to be drawn and sent to the central laboratory according to the local procedure for evaluation of haematology, clinical chemistry, urinalysis and HbA1c, FPG, fasting insulin, C-peptide and glucagon.
- A serum pregnancy test is to be performed in females with childbearing potential.
- Evaluation for any AEs including hypoglycaemic episodes experienced by the subjects since last visit
- Review and final collection of subject diary
- Unused MP-513 or placebo has to be returned to the site.

Follow-up Visit (Week 26 plus 14 days following completion / Early termination of double-blind treatment period)

Two weeks after end of treatment, a telephone follow-up visit will take place to ask the subjects about any AEs including hypoglycaemic episodes experienced by the subjects since the last visit and use of concomitant treatments.

- Review of the use of the regular metformin therapy.

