However, medical judgement has to be exercised in deciding whether an event is serious in any other situations considered medically relevant.

The evaluation of the AE as serious or not-serious is made independently of any attribution of causality.

Events NOT considered to be SAEs are those that require:

- treatment, which is elective or pre-planned, for a pre-existing condition that is unrelated to the indication under study and does not worsen
- treatment on an emergency, outpatient basis for an event NOT fulfilling any of the definitions of serious given above and NOT resulting in hospital admission for the purpose of this study, a hospitalisation is defined as a hospital stay of at least 8 hours and/or an overnight stay).

AE severity

AE severity determined by the clinical investigator on the basis of his/her direct observations or the subject's reporting:

- Mild: causes no limitation of usual activities; the subject may experience slight discomfort
- Moderate: causes some limitation of usual activities; the subject may experience annoying discomfort
- Severe: causes inability to carry out usual activities; the subject may experience intolerable discomfort or pain.

AE causality (relationship guide)

Any AE has to be judged for causality (relationship to study medication).

The relationship of an AE to the study product is to be graded on the basis of the following:

• Reasonable possibility	The relationship of the clinical event to the investigational product administration is “related”, “possible related”, “Possibly not related” or “unassessable” will be regarded as “reasonable possibility”.
• No reasonable possibility	The relationship of the clinical event to the investigational product administration is “not related” will be regarded as “no reasonable possibility”.

Handling of AEs

If an AE occurs, appropriate diagnostic and therapeutic measures are to be taken and the study product has to be discontinued if appropriate. Follow-up evaluations of the subject are to be performed, whenever possible, until the subject recovers or until the investigator considers the situation to be no longer clinically significant.

If clinically significant laboratory abnormalities appear at Week 24 or Early termination visit, appropriate additional tests may be performed to clarify the nature of any clinically significant laboratory abnormalities that occur. If an abnormal laboratory

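### The Week 24 window rule can let an unscheduled off-treatment repeat replace the end-of-treatment value when Visit 6 falls on Days 161–167

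*SAP*

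**What the plan says.** SAP 6.2.2 sets one algorithm for efficacy and safety: "all scheduled and unscheduled clinic visits will be windowed as presented in the below table". The row for the endpoint visit reads "Visit 6 Week 24 168 161 – 175", that is, target Day 168 and window Days 161–175. Where a window holds more than one assessment, "the data from the visit closest to the scheduled study day will be used". For ties: "If two visits have the same distance from the scheduled study day, the data of the visit after the scheduled study day will be used". In making this choice the section does not separate scheduled from unscheduled visits and does not mention the last dose. It also lets unscheduled assessments feed LOCF at Weeks 12 and 24.

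Of Visit 6, Protocol 6.6.1 says: "This visit is the regular end of treatment visit". The visit is allowed within 7 days either side of Week 24, so treatment may end from Day 161. The visit text has unused drug returned, and SAP 6.6 counts exposure up to the date of Visit 6. Afterwards, under Protocol 6.5.3, "Subjects may change the dosage and/or the dose regimen after the final dose of the study drug".

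The only data cut-off in the SAP is in 7.3 and concerns subjects who discontinue. The follow-up visit is by telephone.

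**The concern.** A completer seen early in the window has a planned end-of-treatment measurement and nothing missing. The Week 24 window nevertheless stays open for up to 14 days after treatment has stopped. An unscheduled repeat of the same measure that lies nearer to Day 168, or equally near on the later side, is then taken as the Week 24 value.

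That value would be off study drug and might also reflect a metformin change. It would enter the LOCF ANCOVA and the supportive MMRM as an ordinary observed Week 24 value, so the MMRM is no check on the problem. The secondary endpoint (FPG) and the other Week 24 endpoints use the same windows. In the MP-513 arm the result would be some dilution of the treatment difference. Where the repeat was prompted by an abnormal value, the substitution would also depend on the outcome.

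**Working it through.** **Inputs.** Target Day 168, window Days 161–175, closest-day rule and later-visit tie rule (SAP 6.2.2). Visit 6 is the end of treatment, Week 24 ± 7 days (Protocol 6.6.1). Difference 0.5, SD 1.0, two-sided 0.05, 90% power, 86 per group (SAP 4.5). The last dose is assumed to be at Visit 6.

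**The plan's own figure.** The normal approximation gives n = 2 × (1.960 + 1.282)² × (1.0/0.5)² ≈ 84.1, so 85 per group. The two-sample t-test needs 85.03, so 86. The SAP's 86 is reproduced and is not in dispute; power at 86 per group is 90.3%.

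**When the repeat wins.** For Visit 6 on day d < 168, any later day up to 168 is closer. A day r beyond 168 is closer or tied if r − 168 ≤ 168 − d, that is, r ≤ 336 − d. The condition is therefore d < r ≤ 336 − d.

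| Visit 6 day | Last repeat day that replaces it | Maximum days off drug | Replacing days / later days in window |
|---|---|---|---|
| 161 | 175 | 14 | 14/14 |
| 162 | 174 | 12 | 12/13 |
| 163 | 173 | 10 | 10/12 |
| 164 | 172 | 8 | 8/11 |
| 165 | 171 | 6 | 6/10 |
| 166 | 170 | 4 | 4/9 |
| 167 | 169 | 2 | 2/8 |
| 168–175 | none | – | 0 |

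Of the 77 day pairs with Visit 6 before Day 168, 56 (73%) replace Visit 6 and 21 do not. This counts possible pairs; it is not a probability. Examples: (162, 169) selects Day 169; (165, 171) is a tie and selects Day 171; (163, 175) keeps Visit 6.

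**By lag.** With a repeat L days after Visit 6, replacement needs d ≤ (336 − L)/2. For L = 3, 5, 7 and 10 this gives d up to 166, 165, 164 and 163, or 6, 5, 4 and 3 of the 15 window days. If Visit 6 dates were spread evenly (assumption), these are 40%, 33%, 27% and 20%.

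**Illustrative size (assumptions, not in the documents).** Suppose 2–10% of completers had a repeat of the relevant measure.
- Share affected: from 2% × 20% = 0.4% to 10% × 40% = 4%.
- HbA1c, if each affected MP-513 subject lost 10–50% of a 0.5 effect: the difference falls by 0.5 × 0.004 × 0.10 = 0.0002 to 0.5 × 0.04 × 0.50 = 0.01 percentage points. Power at 86 per group moves from 90.3% to between 90.3% and 89.2%.
- FPG, if the effect were wholly lost in affected subjects: it shrinks by the same 0.4–4%.

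A stress case outside that range, with 10% of MP-513 subjects displaced and half the effect lost, gives a difference of 0.475 and power of 87.2%.

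**The case against.** The strongest reply is that little in the plan would generate such a repeat. Protocol 6.6.2.4 does say that after an abnormal Week 24 result "appropriate additional tests may be performed to clarify the nature of any clinically significant laboratory abnormalities that occur". But that clause belongs to adverse-event handling. The safety panel it serves, there and in SAP Table 5, contains no HbA1c, plasma glucose, insulin, C-peptide or glucagon; glucose appears only in urinalysis. A repeat liver enzyme displaces no efficacy value. The FPG discontinuation thresholds in Protocol 6.3.3 stop short of Week 24, so they prompt no recheck. This stands: a reader might infer that the additional-tests clause produces repeat HbA1c or FPG samples, but the documents permit such repeats without calling for them.

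It can also be said that SAP 6.7 ties efficacy sampling to scheduled visits, and that the only use SAP 6.2.2 spells out for unscheduled values is LOCF. That shows a possible intent but does not settle the matter, because the opening sentence of 6.2.2 expressly windows unscheduled visits for effectiveness.

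Confounding is also limited. The listed anti-diabetic drugs stay prohibited for 2 weeks after the final dose (Protocol 6.5.1), which leaves metformin as the main possible change. Finally, the rule is pre-specified and treatment-blind, and any dilution works against the drug in a superiority test. All of this stands and bears on size. None of it gives Visit 6 priority.

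**Conclusion.** The gap in the rule is real but conditional. It needs a completer with Visit 6 on Days 161–167 and an unscheduled repeat of the same efficacy measure with d < r ≤ 336 − d. A reader might infer that any repeat after an early Visit 6 displaces it; 21 of the 77 day pairs do not.

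Nor do the documents support reading this as a material threat to the primary result. No repeat rate is given, and the 2–10% used above is an assumption. Time off drug is at most 14 days, so a loss of the full treatment effect in each affected subject cannot be presumed. The expected effect on HbA1c is negligible and toward the null. Greater exposure of FPG is plausible but also assumed.

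The case for acting is that the stated rule can discard the protocol's own end-of-treatment measurement in a subject with no missing data, and that preventing this costs almost nothing.

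**What to change.** In SAP 6.2.2 state that, for efficacy variables:
- the scheduled visit's value is used whenever it lies in the window;
- an unscheduled value is used only if the scheduled one is missing;
- values taken after Visit 6 or the early termination visit are not eligible for Week 24 or for LOCF.

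If a limit tied to the last dose is wanted as well, it should be a single pre-specified limit consistent with the early termination visit, which Protocol 6.6.1 allows up to 7 days after the decision to stop. A one-day limit, for example, has no basis in the documents and would not fit that visit.

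Separately, Table 2 in both documents appears to mark dispensing at Visit 6, whereas the Visit 6 text in Protocol 6.6.1 lists only return of unused drug. These must be reconciled so that the end of treatment is clear.

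The cost is a short SAP addition and a date check in the derivation program. No scheduled on-treatment value is lost and the sample size is unchanged. One consequence to accept knowingly is that a redraw after Visit 6 for a spoiled sample would not count, so that subject's value would be carried forward from an earlier assessment.
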